## **10.4 Study monitoring and auditing**

### **10.4.1 Investigator responsibilities**

Investigator responsibilities are set out in the ICH guideline for Good Clinical Practice (GCP) and in the US Code of Federal Regulations.

Investigators must enter study data onto CRFs or other data collection system. The Investigator will permit study-related audits by Celgene or its representatives, IRB/EC review, and regulatory inspection(s) (e.g., FDA, EMEA, TPP), providing direct access to the facilities where the study took place, to source documents, to CRFs, and to all other study documents.

The Investigator, or a designated member of the Investigator's staff, must be available at some time during audit visits to review data and resolve any queries and to allow direct access to the subject's records (e.g., medical records, office charts, hospital charts, and study related charts) for source data verification. The data collection must be completed prior to each visit and be made available to the Celgene representative so that the accuracy and completeness may be checked.

## 11 Biostatistical Analysis

### 11.1 Overview

The aim of the study is to compare the diagnostic ability of the gold standard microarray assay to the Luminex Bead assay and to quantitative real-time PCR assay in order to detect Revlimid®-response in patients with MDS. Earlier studies have shown microarray assay to identify responders with a sensitivity of 94% and a specificity of 86% (44). It is hypothesized that the less expensive and more clinically useful Luminex Bead assay will predict MDS Revlimid® responders with a sensitivity of 75% and a specificity of 70% compared to criterion gold standard microarray assay. However, it may be possible that real-time PCR will also be equally useful clinically and an easier assay to perform in the clinical lab setting as many pathology laboratories are now equipped with the necessary instrumentation. We will thus compare both the Luminex and real-time PCR assays, assuming the same level of sensitivity and specificity for each, to the gold standard microarray assay. These levels would be 80% of the sensitivity and specificity of the gold standard.

To test this hypothesis, a paired design will be used with each subject being tested with both diagnostic tests [microarray versus either Luminex or PCR; (written "Luminex" in the formula)]. The null hypothesis is that the difference in sensitivity rates will be more than 0.80, and the alternative hypothesis will be that the difference in rates will be less or equal to 0.80. Using the sample size formula:

$$n = \left( \frac{z_{(1-\beta)} + z_{(1-\alpha)}}{\log(\gamma/\delta)} \right)^2 \left( \frac{(\gamma+1)TPR(luminex) - 2(concordance\ probability)}{\gamma(TPR\ luminex)^2} \right)$$

Where  $1-\beta$  is the power (0.80) and  $\alpha$  is the Type I error rate (0.95),  $\delta$  is the percentage difference between the microarray assay true positive rate (TPR) and the luminex TPR. The concordance probability is the estimated percentage of both tests having concordant true positives. Using the estimated concordance of 50%, an estimated 100 subjects will be required. With concordance set at 60%, an estimated 59 subjects will be required. (Alonso, T Sample size calculations for comparative studies of medical tests for detecting presence of disease. Stats in medicine 2002; 21:835-852)

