### **5 Study Objectives and Endpoints**

#### **5.1 Objectives**

##### **5.1.1 Primary Objective**

To conduct a prospective trial testing the Revlimid® (lenalidomide) response signature in patients who have transfusion dependent, non-del(5q), low and intermediate-1 risk myelodysplastic syndromes (MDS) in order to confirm the predictive value of the signature and to establish the boundaries of the z-score which can be used to pre-select patients in future clinical studies.

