## **5.2 Endpoints**

### **5.2.1 Primary Endpoint**

- Assessment of pre-therapy gene expression profile associated with Revlimid® responsiveness.

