### **11.3 Assessment of pre-therapy expression profile associated with Revlimid® responsiveness**

Bone marrow samples will be collected and stored in the laboratory of [name] for gene expression analysis.

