### **11.4 Microarray analysis**

Microarray analysis will be performed on RNA purified from mononuclear cells using Trizol (Invitrogen). Linear amplification of 20 ng of total RNA will be performed using the Ovation Biotin RNA Amplification and Labeling System (Nugen, Inc.). Fragmented, labeled cDNA will be hybridized to Affymetrix HG\_U133 Plus 2.0 oligonucleotide microarrays as described by the manufacturer. Raw expression values will be normalized using Robust Multiarray Averaging (RMA) (41). The genes to be analyzed in this trial are the same genes that were identified in Plos Medicine (44).

**Ligation-mediated amplification and Luminex detection:** All MDS patients enrolled in the Revlimid® protocol described below will have their pre-therapy bone marrow mononuclear cells stored in [name] laboratory at Columbia University Medical Center. Total RNA from bone marrow mononuclear cells preserved in Trizol will be used for the Luminex assay the expression of 32 genes, which includes the 24 genes of interest and controls will be evaluated using multiplexed ligation mediated amplification (LMA).

For each transcript, two LMA probes have been designed. The upstream probe contains a T7 universal primer sequenced, one of 32 different barcodes (Tm Bioscience, [www.universalarray.com](http://www.universalarray.com)), and a 20 nucleotide gene specific sequence. The downstream probes are 5' phosphorylated, and contain a 20 nucleotide sequence contiguous with the gene-specific fragment of the upstream probe and a T3 universal primer site. Gene specific probe sequences are unique to the target gene when compared to the Human RefSeq database, have similar base composition, and target the 3' end of the target genes.

Prior to LMA, 100 ng/well of total RNA will be applied to oligo-dT coated plates (GenePlateHT, RNAture) in Lysis Buffer (RNAture). Bound, poly(A) RNA will be reverse transcribed using Superscript II (Invitrogen). LMA probes will be annealed to their target cDNAs and ligated by *Taq* DNA ligase (New England Biolabs). Ligation products, all 104 nucleotides in length, will be amplified by 34 cycles of PCR using T3 and 5'-biotinylated T7 primers. Amplicons will be detected using fluorescent microspheres of 32 different colors (xMAP Multi-Analyte COOH Microspheres, Luminex). Microspheres of each color are covalently coupled to a unique capture probe complementary to one of the 32 gene-specific barcodes. Following labeling of the biotinylated amplicons with

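### Section 11 states no analysis, cut-off rule or success criterion for the primary objective; its only formal test compares the sensitivities of two assays, which cannot show that the signature predicts response

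*Combined protocol and SAP*

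**What the plan says.** - **Objective and endpoint.** Section 5.1.1, repeated in the Synopsis, makes it primary "to confirm the predictive value of the signature and to establish the boundaries of the z-score", for use in selecting patients for later studies. The primary endpoint in 5.2.1 is "Assessment of pre-therapy gene expression profile associated with" Revlimid responsiveness.
- **11.1.** The overview opens with "The aim of the study is to compare the diagnostic ability of the gold standard microarray assay to the Luminex Bead assay", then adds real-time PCR. It cites 94% sensitivity and 86% specificity for the microarray from earlier work and hypothesises that Luminex will predict responders "with a sensitivity of 75% and a specificity of 70% compared to criterion gold standard microarray assay". It then says: "These levels would be 80% of the sensitivity and specificity of the gold standard". The formal statement is: "The null hypothesis is that the difference in sensitivity rates will be more than 0.80", with the alternative at or below 0.80.
- **11.2.** The proportion achieving transfusion independence is reported with an exact 95% interval. The signature is not involved.
- **11.3.** This section carries the title of the primary endpoint. Its whole content is one sentence beginning "Bone marrow samples will be collected and stored in the laboratory of".
- **11.4.** The gene set is fixed ("The genes to be analyzed in this trial are the same genes that were identified in Plos Medicine"), and normalisation and laboratory steps are described. No scoring rule or cut-off is given.
- **11.5.** Safety only.

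The term z-score does not appear anywhere in Section 11.

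**The concern.** The objective asks two things: does the signature separate responders from non-responders in non-del(5q) patients, and where should the z-score cut-offs lie? Section 11 answers neither and plans a comparison between assays instead. The trial could therefore be run exactly as written, meet its one formal hypothesis, and leave the primary objective unanswered.

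This matters for two reasons. Section 4.8 gives the benefit of the signature as sparing patients who are unlikely to respond. That depends on recognising non-responders, which sensitivity does not measure. The question is also open in this population: the earlier test set in Section 4.8 mixed patients with and without del(5q), while this trial enrols only those without. A boundary set here is meant to select patients in future studies, so an over-optimistic one would carry forward.

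**Working it through.** **1. The plan's own figure.** The only computed figure in Section 11 is the sample size for the paired sensitivity comparison: 100 subjects at 50% concordance and 59 at 60%. The 11.1 formula is n = [(z₁₋β + z₁₋α)/log(γ/δ)]² × [(γ+1)TPR − 2c]/(γ·TPR²). I took power 0.80, one-sided α = 0.05 (0.95 is printed), TPR = 0.75, δ = 0.80 and γ = 1 (γ is not defined in the text).

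- First factor: [(0.842 + 1.645)/0.223]² = 124.2.
- c = 0.50: 124.2 × (1.5 − 1.0)/0.5625 = 110.4, against 100.
- c = 0.60: 124.2 × (1.5 − 1.2)/0.5625 = 66.2, against 59.

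δ = 0.79 gives 98.9 and 59.3, close to both, but 0.79 is not in the documents. The planned total is 56. Nothing below depends on this mismatch. The relevant fact is that the calculation sizes an assay comparison and nothing is sized for the primary objective.

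**2. Objective against analysis.**

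| Needed for 5.1.1 / 5.2.1 | Found in Section 11 |
|---|---|
| Estimate and interval for signature against response | None planned; 94%/86% and 75%/70% are prior or hypothesised values |
| Test or success criterion for prediction | None; the one null/alternative is relative sensitivity |
| Specificity | Hypothesised at 70%; no test or interval |
| Scoring rule and z-score boundary | Not stated |

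**3. What the formal test can establish.** Take clinical response as the reference.

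- Both assays call every patient positive: sensitivities 100% and 100%, ratio 1.00, difference 0, specificity 0%.
- Both assays make identical calls, positive in 40% of responders and 40% of non-responders: ratio 40/40 = 1.00, difference 0, sensitivity 40%, specificity 60%. Calls are unrelated to response.

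Both cases satisfy the null/alternative statement, whether 0.80 is read as a ratio (at least 0.80) or literally as a difference (at most 0.80). This is exact and needs no assumption about agreement between assays. If the microarray is the reference instead, clinical response does not enter the comparison at all.

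**4. Which reference standard?** The phrase comparing Luminex with the criterion microarray points to the microarray. The arithmetic points to response: 0.80 × 94% = 75.2% and 0.80 × 86% = 68.8%, close to the stated 75% and 70%, and 94%/86% are described as performance in identifying responders. The section does not settle it.

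**5. Precision available at N=56.** Section 4.7 reports transfusion independence in 56 of 214 non-del(5q) patients (26%). Expected responders: 56 × 56/214 = 14.7, with a 95% binomial range of 8 to 21. Exact (Clopper–Pearson) 95% intervals near 94% sensitivity and 86% specificity:

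| Responders / non-responders | Sensitivity | Specificity |
|---|---|---|
| 8 / 48 | 8/8: 63–100% | 41/48: 72–94% |
| 15 / 41 | 14/15: 68–100% | 35/41: 71–94% |
| 21 / 35 | 20/21: 76–100% | 30/35: 70–95% |

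If haematological improvement is the response (92 of 214, 43%), about 24 responders are expected: 23/24 gives 79–100% and 28/32 gives 71–97%.

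**The case against.** **Section 11.1 does name performance levels.** It hypothesises 75% and 70% and introduces the paired design as the way to test that hypothesis. A reader might infer from the two examples above that a useless signature satisfies all of 11.1. The documents do not support that: with response as reference, an all-positive assay has 0% specificity against a hypothesised 70%, and the 40%/60% assay misses both levels. What stands is narrower. The levels carry no test or interval, and the formal null/alternative covers relative sensitivity only. Sensitivities against response might be computed on the way to that comparison, but the plan does not say that they will be reported or judged.

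**A scoring rule may exist elsewhere.** Section 11.4 takes its genes from a cited publication, and Section 4.8 says that the three platforms were analysed by identical methods. A reader might infer that no rule exists. All that can be said is that none is stated in these documents.

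**Setting boundaries in this trial is its purpose.** A reader might infer that the cut-off will be chosen and judged in the same 56 patients. The plan does not say so, and deriving the boundary here is what 5.1.1 intends. The gap is that nothing says how its performance will be assessed.

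**How often would a useless signature pass?** A single probability is tempting, but it depends on the agreement between assays and on the positive-call rate against response, neither of which the documents give. None is claimed.

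**Conclusion.** The point holds and should be corrected before analysis. The primary objective has no stated analysis, interval, cut-off rule or success criterion in Section 11, and the one formal test can be satisfied with a sensitivity ratio of 1.00 and a specificity of 0%. This rests on the text and on exact arithmetic; no response rate or agreement figure is assumed. Masked or removed text does not explain the gap, since only a laboratory name is masked in 11.3.

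The precision figures do rest on assumptions: all 56 patients evaluable, a response rate like the earlier trial's 26%, and true performance near 94%/86%. The unclear reference standard is a related wording fault that the same revision can settle.

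**What to change.** Rewrite 11.1 and 11.3 as follows.

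- **Primary analysis.** The microarray signature score against clinical response, in all treated patients with an evaluable pre-therapy marrow assay. Report the number without one.
- **Response.** Transfusion independence, already the primary clinical efficacy parameter in 5.1.2 and 8.1. Repeat with IWG haematological improvement as a sensitivity analysis.
- **Score.** Lock the scoring rule before response data are examined.
- **Reporting and success.** Sensitivity and specificity with exact 95% intervals, and a pre-stated criterion that includes specificity. AUC with its 95% interval is one option for a global measure, but an AUC above 0.50 would not by itself show that non-responders are identified.
- **Boundary.** Derive the z-score boundary in this trial as intended, and report its performance with cross-validated or bootstrap optimism correction.
- **Reference standard.** Name clinical response for all three assays, and make Luminex and PCR against microarray secondary.
- **Sample size.** Replace the present justification with expected precision at N=56 across 8 to 21 responders.

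The cost is a rewrite of two subsections; no new samples, assays or visits are needed. The drawbacks are that the stated precision is modest, especially near 8 responders, and that the assay comparison loses its place as the leading analysis.

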**Initial microarray data was available on 8 responders and 8 non-responders who did not have the del(5q). (the “training” set).** There was a very distinct pattern of gene expression that separated the responders from non-responders. Equally exciting was the observation that among the 100 ranked genes of interest in the heat-map were groups of genes that have previously been shown to be associated with MDS pathology. It seems that a number of genes involved in erythropoiesis are clearly under-expressed in patients, including all of the responders. For example HBA1 (alpha1 globin), ankyrin1 erythrocytic, dematin or EPB 49 (erythrocyte membrane protein band 49), EPB3 (red cell anion exchanger), ferrochelatase, hemoglobin alpha 2/DEF (human alpha globin gene with flanks), human sickle cell beta globin, Kidd blood group (SLC14A1) are genes that are under-expressed in the cells of the responders. This expression signature can be used for predicting which patients have a chance to respond versus those who definitely will not benefit. However, the DNA microarray technology cannot be easily adapted for prospective clinical testing in a timely fashion. Two simpler assays to measure gene expression currently used by

clinical labs are quantitative real time PCR and the Luminex bead hybridization assay. The relative ease of use and cost of these assays will allow them to be easily implemented in a clinical setting in the future. This bead based technology is being rapidly developed for clinical, research and diagnostic purposes. It is less complex than microarray analysis, and can analyze the expression of up to a hundred genes in a single well, making it easier to use in the clinical diagnostic setting. The results with the Luminex assay gave essentially the same results as the Affymetrix chips, and better results than the TaqMan. Identical methodology for analysis of Affymetrix, TaqMan qPCR and Luminex data were used. Thus Luminex **may** be adaptable to the broader clinical setting.

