streptavidin-coated phycoerythrin, the labeled amplicons will be annealed to capture probe-linked fluorescent microspheres. Microspheres are detected by flow cytometry and captured labeled amplicons are quantified (Luminex) by subtracting background from the mean fluorescent intensity of each bead.

**Real-time PCR:** Total RNA from bone marrow mononuclear cells preserved in Trizol will be used for the Real-time PCR assay for the expression of 32 genes, which includes the 24 genes of interest and controls. Primers for each gene will be designed (Roche Biosystems) such that only the RNA transcript and no genomic DNA will be measured by the Roche Light Cycler quantitative PCR assay. The Sybergreen kit (Roche) which measures relative amount of gene specific transcript will be used. Results will be analyzed with the Roche Light Cycler analysis package.

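### Section 11.1 sizes the Luminex and PCR comparisons with one calculation on an unsupported equal-accuracy assumption, so its 80% power cannot be claimed for PCR and is not established for Luminex either

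*Combined protocol and SAP*

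**What the plan says.** Section 11.1 of the combined protocol and SAP makes the comparison of Luminex and real-time PCR with the microarray the aim of the study.

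- Microarray: "Earlier studies have shown microarray assay to identify responders with a sensitivity of 94% and a specificity of 86"%.
- Luminex: it "will predict MDS Revlimid® responders with a sensitivity of 75% and a specificity of 70% compared to criterion gold standard microarray assay".
- PCR: it has no figure of its own. The reason for including it is that "it may be possible that real-time PCR will also be equally useful clinically", and it is planned "assuming the same level of sensitivity and specificity for each".
- Common level: "These levels would be 80% of the sensitivity and specificity of the gold standard".

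One formula follows, in which the Luminex term stands for either assay. Power is 0.80 and the boundary 0.80. The result is 100 subjects at 50% concordance and 59 at 60%. Section 11.2 plans 56 patients.

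Two other places bear on this. Section 4.8 reports that Luminex gave "essentially the same results as the Affymetrix chips, and better results than the TaqMan", without rates. The real-time PCR text in section 11.4 specifies a different PCR chemistry: "The Sybergreen kit (Roche) which measures relative amount of gene specific transcript will be used". No accuracy is given for it.

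**The concern.** A calculation made once can serve two comparisons only if both assays have the same expected ratio to the microarray. The only comparative statement in the documents ranks the two assays differently, and section 11.1 neither mentions nor reconciles it.

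The test sets a sensitivity ratio against a margin, and the number needed rises steeply as the true ratio falls from 1 toward that margin. A modest shortfall of PCR relative to Luminex could therefore take most of the power from the PCR comparison while the plan still shows 80% for both. A non-significant PCR result might then be taken as evidence against PCR when the study could not have shown otherwise.

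**Working it through.** **Inputs.** Section 11.1: microarray sensitivity 0.94, Luminex 0.75, power 0.80, boundary delta 0.80, concordance 0.50 and 0.60. The Type I error is printed as 0.95; I read it as alpha 0.05, one-sided because the formula uses z(1−alpha). The boundary is called a difference; I read it as a ratio, because the formula takes log(gamma/delta). Gamma has no definition or value. Section 4.7: in the earlier non-del(5q) trial 26% became transfusion independent and 43% had hematological improvement.

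**Step 1: the plan's own figures.** (0.842 + 1.645)² = 6.183. The nearest reading from printed inputs is gamma = 1, TPR = 0.75, delta = 0.80:

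- ln(1/0.80)² = 0.0498, and 6.183/0.0498 = 124.2.
- Concordance 0.50: 124.2 × (1.50 − 1.00)/0.5625 = 110.4, against 100 stated.
- Concordance 0.60: 124.2 × (1.50 − 1.20)/0.5625 = 66.2, against 59 stated.

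At the stated sizes, power on this reading is about 76%. Other readings are no closer on both figures: gamma = 0.94/0.75 with delta 0.80 gives 30.0 and 21.3, and gamma = 0.80 with delta 1 gives 96.6 and 41.4. Delta = 0.79 gives 98.9 and 59.3, but 0.79 is not in the documents.

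**Step 2: the planning values taken literally.** 0.75/0.94 = 0.798, so log(gamma/delta) is about zero and no usable size exists. Power is about 5% at 56, 59 or 100, for either assay. The printed concordances are also impossible with sensitivities of 0.94 and 0.75, since joint true positives must be at least 0.94 + 0.75 − 1 = 0.69. Gamma = 1 with TPR 0.75 avoids this only by giving the microarray 75% as well.

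**Step 3: sensitivity to the ratio.** Keep the Step 1 reading and lower gamma, taken as new assay over reference with 0.75 as the reference rate:

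| Gamma | n at concordance 0.50 / 0.60 | Power at 100 / 59 |
|---|---|---|
| 1.00 | 110.4 / 66.2 | 76% / 76% |
| 0.95 | 181.2 / 102.8 | 58% / 59% |
| 0.90 | 374.1 / 198.1 | 36% / 39% |

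**Step 4: power at the responders expected.** Sensitivity is estimated in responders only: 0.26 × 56 = 14.6 and 0.43 × 56 = 24.1, so about 15 to 24. Let B = 0.94, A = r × 0.94 and c = joint true positives:

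- v = (A + B − 2c)/(A × B)
- responders needed = 6.183 × v / ln(r/0.80)²
- power with m responders = Φ[ln(r/0.80)/√(v/m) − 1.645]

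The lowest feasible c is A + B − 1 and the highest is A. At r = 1.0 the highest value makes v zero, so c = 0.92 is used there.

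Example, r = 0.90, lowest c: A = 0.846, c = 0.786, v = (1.786 − 1.572)/0.795 = 0.269. With m = 15, 0.1178/√(0.269/15) = 0.88, and Φ(0.88 − 1.645) = 22%.

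| True ratio r | Responders needed (highest to lowest c) | Power, 15 responders, lowest c | Power, 24 responders, highest c |
|---|---|---|---|
| 1.00 | 6 to 17 | 76% | over 99% |
| 0.95 | 12 to 42 | 44% | 97% |
| 0.90 | 53 to 120 | 22% | 51% |
| 0.85 | 316 to 585 | 11% | 17% |

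These are large-sample approximations. At r = 1.0, c = 0.88 and 15 responders, only 0.12 × 15 = 1.8 discordant patients are expected, so the figures show order of size and not exact power.

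**The case against.** The best defence is that section 4.8 only ranks the assays. It gives no sensitivity, specificity or sample count. The planning value of 75% lies far below a Luminex that matches a 94% microarray, so PCR could be worse than Luminex and still reach 75%. The ranking also concerns TaqMan, while the trial uses SYBR Green on a different platform, so the evidence on PCR is indirect. At a ratio of 0.95 with the highest concordance, PCR power would be 88% with 15 responders and 97% with 24. Finally, section 11.1 sets no rule for rejecting PCR after a non-significant result, and section 5.2.1 names assessment of the expression profile as the primary endpoint.

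Much of this stands. A reader might infer that the documents show the PCR comparison to be underpowered; they do not. They leave PCR accuracy unknown, and the loss of power is a sensitivity of the calculation. Misreading of a null PCR result is likewise a risk and not something the plan prescribes.

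The defence does not rescue the shared calculation. Reaching 75% is not enough, because 75% is a ratio of 0.798, where no size gives useful power. The reading nearest to 100 and 59 needs a ratio of 1. Section 4.8 lends qualitative support to that for Luminex and none for PCR.

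**Conclusion.** The point holds as a gap in justification, with a potentially large effect. One calculation covers two assays on an equality that the documents do not support, and a 5% to 10% shortfall in the ratio lowers power at the stated sizes from about 76% to between 36% and 59% on the nearest reading. The 80% power therefore cannot be claimed for PCR on the strength of the Luminex calculation.

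A reader might also infer that the 80% is sound for Luminex and fails only for PCR. The documents do not support that. The assumed ratio lies at the boundary, gamma is undefined, the stated sizes do not reproduce, and section 4.8 gives no rate from which a Luminex ratio could be set. Even an assay equal to the microarray would have only about 76% power with 15 responders at the lowest feasible concordance.

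The power ranges rest on a ratio margin of 0.80, one-sided 0.05, microarray sensitivity 94%, sensitivity defined against clinical response, and 26% to 43% responders among 56. All the true ratios are assumptions.

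**What to change.** - For Luminex and PCR separately, define gamma and delta and state the expected sensitivity and a concordance that is feasible with the two sensitivities. Give the ratio of each assay to the microarray as a range.
- Replace the shared 80% by the power of each comparison at the expected number of responders among 56, over that range.
- Where a comparison falls short, designate it in advance as estimation: the paired sensitivity ratio with its confidence interval. Add that a non-significant result is not evidence against the assay.

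The cost is a recalculation and revised wording in section 11.1, and probably a less favourable stated power. No patients are added.

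### Section 11.1 misstates the plan's only hypothesis test, and its 100 and 59 subjects at 80% power do not follow from the stated 75% and 94% sensitivities

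*Combined protocol and SAP*

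**What the plan says.** Section 11.1 (Overview) describes a paired comparison of microarray with Luminex or real-time PCR.

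- Expected performance of microarray: "Earlier studies have shown microarray assay to identify responders with a sensitivity of 94% and a specificity of 86"%.
- Expected performance of Luminex, with PCR assumed the same: "responders with a sensitivity of 75% and a specificity of 70"%, a phrase the plan then sets against microarray as criterion. It adds: "These levels would be 80% of the sensitivity and specificity of the gold standard".
- Null hypothesis: "The null hypothesis is that the difference in sensitivity rates will be more than 0.80".
- Alternative, on the same scale and with the same number: "the alternative hypothesis will be that the difference in rates will be less or equal to 0.80".
- Formula inputs: power is 0.80; alpha "is the Type I error rate (0.95"). Gamma appears in the formula but is not defined, while delta "is the percentage difference between the microarray assay true positive rate (TPR) and the luminex TPR". Concordance is the proportion in which both tests are true positives.
- Result: "Using the estimated concordance of 50%, an estimated 100 subjects will be required"; at 60% concordance the figure is 59.

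The synopsis and sections 5.2.2, 6.2 and 11.2 plan 56 patients. Section 11.2 offers a transfusion-independence proportion with an exact confidence interval and response percentages, but no test.

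**The concern.** The stated hypotheses match no usable test. The number 0.80 is attached to a difference, while the neighbouring sentence and the formula both work with ratios. The sample sizes do not look like products of the stated sensitivities, and the concordances look too low for two assays of 75% and 94%. The expected ratio also appears to equal the margin, which would leave almost no power.

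This section is the only place where the plan says what about 56 patients can establish about Luminex or PCR. If it cannot be executed, the analyst must guess the hypothesis, and the reader cannot interpret the 80% power claim.

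**Working it through.** **Inputs.** From section 11.1: sensitivities 0.94 (microarray) and 0.75 (Luminex), concordance c = 0.50 or 0.60, power 0.80. Alpha is taken as one-sided 0.05, since 0.95 is evidently 1 − alpha and the formula uses z(1−alpha). From section 4.7 (non-del(5q) trial): 26% transfusion independence and 43% hematological improvement. That these rates apply here is an assumption: 56 × 0.26 = 14.6, about 15 responders; 56 × 0.43 = 24.1, about 24.

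**1. The margin on each scale.**
- Difference: 0.94 − 0.80 = 0.14, so a sensitivity of 14% satisfies the alternative.
- Luminex/microarray ratio: 0.80 is a sensible margin, but success as written would show that Luminex is worse.
- Microarray/Luminex ratio, the printed formula's orientation: the direction is the usual one, but the margin should be 1/0.80 = 1.25. At 0.80 the alternative would need a Luminex sensitivity of 0.94/0.80 = 117.5%.

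**2. Reproducing 100 and 59.** Write T for the Luminex sensitivity and gamma × T for the microarray sensitivity. The formula is then

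n = [(0.842 + 1.645)/ln(gamma/delta)]² × V, with V = (S − 2c)/(product of the two sensitivities),

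where S is the sum of the sensitivities.

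- At 75% and 94%: gamma = 1.253 and V = 0.69/0.705 = 0.979 (c = 0.50) or 0.49/0.705 = 0.695 (c = 0.60). With delta = 0.80, n = 30.0 and 21.3. With delta = 1.25, n exceeds 200,000 at any feasible concordance, because 1.253 sits at the margin.
- The quotient of the two sample sizes is (S − 1.0)/(S − 1.2), whatever alpha, power or delta may be. The plan's is 100/59 = 1.695, so S = 1.488 (1.479 to 1.498 allowing for rounding). The stated S = 1.69 gives 0.69/0.49 = 1.408.
- Equal sensitivities of 0.75 (gamma = 1) with delta = 0.79 give 98.9 and 59.3; with delta = 0.80 they give 110.4 and 66.2. The first is close to the plan's figures but is an inference. Other pairs also fit: 0.83 and 0.66 with ratio margin 0.63 give 102 and 60.

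**3. Feasible concordance.** With response as truth, joint positivity lies between 0.94 + 0.75 − 1 = 0.69 and 0.75, so 0.50 and 0.60 cannot occur. At 75% and 75% the range is 0.50 to 0.75.

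**4. Power of a correctly directed ratio test, margin 0.80.** When the truth lies in the alternative, power = Φ(√(N/V) × |ln(ratio/margin)| − 1.645), with N counted in responders.

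At 75% against 94%, the ratio is 0.75/0.94 = 0.798, just inside the null. For N = 15 to 56 and c = 0.69 to 0.75, power is 4.6% to 4.8% (5% at the unrounded 0.80 × 0.94 = 75.2%). Simulated Wald tests reject in 7% to 8% (N = 56) and 9% to 18% (N = 15); that is inflated size in small samples, not power.

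At equal sensitivities of 75%, V = (1.5 − 2c)/0.5625 and ln(1/0.80) = 0.223:

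| Concordance | V | 15 responders | 24 responders | 56 responders |
|---|---|---|---|---|
| 0.50 (minimum) | 0.889 | 23% | 31% | 55% |
| 0.60 | 0.533 | 32% | 44% | 74% |
| 0.70 | 0.178 | 66% | 83% | 99% |

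Simulation for 15 responders gives 26%, 37% and 68%. With margin 0.79 and 56 responders, the first two rows become 59% and 78%.

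**5. Precision.** The 90% interval is ratio × exp(±1.645 √(V/N)). With 15 responders and a true ratio of 1, it is 0.67 to 1.49 (c = 0.50) or 0.73 to 1.36 (c = 0.60). At 75% against 94%, it runs from 0.60 to 1.06 (c = 0.69) or from 0.64 to 0.99 (c = 0.75).

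**The case against.** Four points can be made for the plan.

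- **The margin is sound and only the wording is not.** A reader might infer that 0.80 fails on every reading. The documents do not support that. As a Luminex/microarray ratio with the inequality turned round, 0.80 gives a coherent non-inferiority test. The fault is in direction and labelling.
- **Power could be adequate.** A reader might also infer that no coherent test reaches 80% with these patients. That does not follow either. At equal sensitivities, 0.50 is the lowest concordance possible, and independent assays would already give 0.75² = 0.5625. Section 4.8 reports close agreement between Luminex and the Affymetrix chips, so high concordance is plausible, and at 0.70 power is 83% with 24 responders. This objection stands: the low figures belong to the plan's own concordances.
- **Sizing at equal rates is ordinary practice.** It is, and 98.9 and 59.3 suggest that it may have been done. But the plan does not say so, and it states 75% against 94%.
- **Microarray may be the reference standard.** The 75% is expressed relative to microarray as criterion. If that is meant, the joint-positivity bounds and responder counts above do not apply as written. The 80% sentence points to response as truth, since 0.80 × 0.94 = 0.752, and a formula comparing two true positive rates needs a separate truth. The ambiguity still has to be settled in the text.

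It is also fair that section 5 makes validation of the signature primary, and that no treatment decision rests on this test.

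**Conclusion.** The concern holds in this form. The hypothesis cannot be used as written, alpha is misprinted, gamma is undefined, and delta is described as a difference but enters as a ratio. The figures 100 and 59 cannot come from 75% and 94%, and, with response as truth, neither can concordances of 50% and 60%.

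The 80% power is unsupported by the plan's own inputs. It is about 5% if 75% against 94% is the expected truth and 0.80 the margin. If equal 75% sensitivities were meant, it is 55% or 74% at the plan's concordances even were all 56 patients responders, and 23% or 32% with 15. It is not unattainable, because power depends strongly on concordance.

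These results assume response as truth, one-sided alpha 0.05, the section 4.7 response rates and a normal approximation that is rough at 15 responders. The transfusion-independence interval in section 11.2 is unaffected.

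**What to change.** Rewrite section 11.1 as follows.

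- State whether clinical response or microarray is the reference standard.
- If it is response, test H0: TPR(assay)/TPR(microarray) ≤ delta0 against H1: > delta0 at one-sided alpha 0.05. Alternatively, keep the microarray/assay orientation with margin 1/delta0.
- Justify delta0 as the minimum acceptable ratio, separately from the ratio expected.
- Define gamma and its orientation, and reconcile it with 75% and 94%.
- Use feasible concordances: 0.69 to 0.75 for 94% and 75%, or 0.50 to 0.75 for 75% and 75%.
- Replace the 100, 59 and 80% statements with power or precision for about 56 patients over a range of responder counts and concordances.
- Report the paired ratio with its two-sided 90% confidence interval.

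The cost is one reworded section and possibly a less favourable power statement, with the comparison perhaps presented as estimation. No new patients or data are needed.
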